4.1 Inclusion Criteria

- Male or female patients with FD age 10 or older
- Unstable blood pressure:
 - Systolic BP standard deviation >15 mmHg
 - Or coefficient of variation >15%
 - Or documented episodic hypertensive peaks (>140mmHa)
- Confirmed diagnosis of FD (Historical confirmation of subjects' genetic diagnosis will be obtained for this study)
- Providing written informed consent (or ascent) to participate in the trial
- Ability to comply with the requirements of the study procedures.

4.2 Exclusion Criteria

- Patients taking MAO-inhibitors
- Patients taking metoclopramide, domperidone, risperidone or other dopamine blockers
- Patients taking tricyclic antidepressants
- Patients taking neuroleptic drugs (haloperidol and chlorpromazine)

CONFIDENTIAL

PHASE II STUDY

Version: 5.0 (date February 12, 2018)

- Patients with a known hypersensitivity to any component of this drug.
- Patients with atrial fibrillation, angina or significant ECG abnormality
- Patients with significant pulmonary, cardiac, liver, renal (creatinine >2.0 mg/ml)
- Patients who have a significant abnormality on clinical examination that may, in the investigator's opinion might jeopardize their healthy participating in this trial.
- Women who are pregnant or lactating.

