The overall study objectives are to determine whether carbidopa (Lodosyn®) is safe and well tolerated and to assess whether it can inhibit catecholamine-induced paroxysmal hypertension and normalize or reduce the exaggerated blood pressure variability in patients with familial dysautonomia (FD, also called hereditary sensory and autonomic neuropathy type III or Riley-Day syndrome).¹

FD is a rare hereditary disorder caused by splice mutations that lead to a deficiency of elongator-1 protein (ELP-1 or IKAP).^{2,3} The defect prevents normal development of sensory (afferent) neurons,⁴ including those that relay information from arterial baroreceptors.⁵ Although reduced in number,⁶ when activated, the remaining efferent sympathetic nerves can dramatically raise blood pressure.^{1,5} Even mild arousals trigger surges in circulating catecholamines levels and characteristic paroxysmal hypertensive episodes.^{1,5,7} Patients also have orthostatic hypotension.

Renal failure is a major problem for patients with FD.⁸ Paroxysmal hypertension and excessive blood pressure fluctuations contribute to the progression of renal damage.^{9,10} Treatment of hypertension in patients with FD is fraught with difficulties. Clonidine and benzodiazepines are currently used to decrease emotionally-induced hypertension ¹¹ but they produce sedation, respiratory depression and dramatically worsen orthostatic hypotension.

We've recently shown that carbidopa, a reversible competitive inhibitor of DOPA-decarboxylase that does not cross the blood brain barrier, 12 successfully blocks the peripheral formation of dopamine and effectively reduced the frequency and severity of the retching/vomiting attacks, a disabling recurrent feature of these patients. 13 In

the small study, carbidopa was well tolerated and safe. New preliminary data indicates that carbidopa also reduces the synthesis of norepinephrine outside the brain in patients with FD. Further exploratory findings suggested that carbidopa might lessen the hypertensive peaks and reduce the exaggerate blood pressure variability over 24-hours, but further evidence is needed.

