chemoreceptors¹⁸ and baroreceptors.⁵ However, there is a relative sparing of efferent sympathetic neurons ¹⁹ which remain functional and release catecholamines.^{5,7} FD patients have a unique autonomic phenotype with periods of paroxysmal hypertension driven by surges in circulating catecholamines. Due to lack of normal baroreflex restrain, arousals result in periods of paroxysmal hypertension and tachycardia throughout the day (Fig.1).⁵ Many patients frequently suffer attacks of nausea and vomiting, as dopamine ⁷ and norepinephrine ⁵ spillover into the circulation. Blood pressure is dramatically unstable in patients with FD. This instability contributes to an overall increase in variability, which appears to be directly related to 24-h norepinephrine excretion (Fig. 2). Although patients with FD also have orthostatic hypotension, ⁵ the most disabling features of the disease are related to heightened sympathetic activity.^{7,10}

[figure not shown]

Fig. 2. Scatterplot shows relationship between NE excretion and BP variability in patients with FD

End-Organ Target Damage:

The main sites of end-organ target damage in patients with FD are the heart ²⁰ and kidneys. ^{8,9} Patients have an increased incidence of renal failure that frequently begins at an early age. ⁸ Twenty-percent of patients that survive to age 25 have end-stage renal disease, requiring dialysis or transplantation. ²¹ Renal biopsies are consistent with chronic hypertensive nephrosclerosis and periods of accelerated hypertension. ⁹ While the underlying cause of the renal failure is unknown, several factors appear to influence its progression. Fludrocortisone, a drug until recently used in the treatment of orthostatic hypotension in patients with FD, ¹¹ dangerously hastens the decline in glomerular filtration rate and is now used sparingly. ¹⁰ As was shown in

hypertensive patients, ^{22,23} FD patients that have higher blood pressure variability (as expressed by the standard deviation [SD] of 24-h ambulatory blood pressure readings) have a greater degree of renal damage. ¹⁰ The same association has been shown in animal models of baroreflex deafferentation. ²⁴ Our recent retrospective analysis (Fig. 3) shows that patients who had the most pronounced blood pressure variability (i.e., the highest SD in 24-h or during the day) had a faster rate of renal decline over the subsequent 13-years of follow-up.

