Patients will be screened for eligibility and enrolled in the trial. Informed consent or ascent will be obtained. Patients will be given a tutorial and provided with written instructions on using the ambulatory blood pressure monitors and 24-h recordings will be obtained. Supine/sitting/standing office blood pressures will be measured. RR-interval and beat-to-beat blood pressure will be recorded for 5 minutes before and during a Stroop test (3-minutes) and during serial 7 subtractions (3 minutes). Patients will be asked to rate their symptoms of orthostatic hypotension on the validated orthostatic hypotension-questionnaire (OH-Q)⁴². Baseline safety bloods (CBC & metabolic panel), a 12-lead ECG and a physical and neurological exam will be obtained. After completing all baseline measures, patients will be randomized to the treatment order sequence (Fig. 6) in a 1:1:1 ratio. For patients that opt to continue follow-up via 2-way telemedicine conferencing, investigators will ensure that the patient has access to a validated blood pressure and heart rate monitor, weighing scale and thermometer at home. These will be provided, if needed. Patients will be given a continuous, automatic, wireless wrist-based heart rate tracker (Fitbit Charge HR, Fitbit, USA), which will be synchronized to allow remote monitoring at the Center. Patients and caregivers will be trained in how to perform a timed active stand test and to obtain blood pressure and heart rate supine (5-min), seated (2-min) and standing (5 min). Written instructions and a video guide will be provided.

Before leaving the office, patients will be instructed to keep a daily symptom diary (a modified version of the Rhodes Nausea/Retching/Vomiting Index³⁹ with additional space to note adverse events). Additionally, patients will be told to contact the Center to report any adverse event. They will be contacted by phone call on the day that they adjust their dose. Seven-days into their treatment arm patients will be contacted again to monitor tolerability and adverse events. Thereafter, we will contact patients on a weekly basis to monitor potential adverse events. They will return for the next study visit in 28-days.

Patients that have been seen at the Center within the last 3-months may have the option of completing the study screening and enrollment proceedures via virtual visits, at the discretion of the PI (a treating investigator).

Visit 2. Crossover #1:

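### The only numeric renal exclusion, in Section 4.2, carries a unit that puts it out of reach (2.0 mg/ml = 200 mg/dL), leaving renal screening to undefined wording and judgement

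*Combined protocol and SAP*

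**What the plan says.** Section 4.2 (Exclusion Criteria) lists, in one bullet, "Patients with significant pulmonary, cardiac, liver, renal (creatinine >2.0 mg/ml". The phrase has no noun after the organ list, so the parenthesis is the only thing that gives renal exclusion a definite meaning. The next bullet is a general one: "Patients who have a significant abnormality on clinical examination that may, in the investigator's opinion might jeopardize their healthy participating in this trial".

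No other section repeats the creatinine limit, expresses it in another unit, or sets an eGFR limit for entry. The Study Summary lists the main inclusion criteria only. Under Visit 1 in Section 6, the plan says "Baseline safety bloods (CBC & metabolic panel), a 12-lead ECG and a physical and neurological exam will be obtained", without a creatinine unit or limit.

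On how common renal disease is, Section 1.1 states "Renal failure is a major problem for patients with FD". Section 1.4 adds "Patients have an increased incidence of renal failure that frequently begins at an early age" and "Twenty-percent of patients that survive to age 25 have end-stage renal disease, requiring dialysis or transplantation".

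**The concern.** A creatinine cut-off in an exclusion list is an operating rule: whoever screens, and later whoever verifies eligibility, compares a laboratory value with it. Written in mg/ml, the cut-off is 100 times what the same number would mean in mg/dL, and a rule set that high has no effect.

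What is at stake is consistent and verifiable screening. Entry is open from age 10 with no upper limit (Section 4.1), so patients with reduced renal function are in the recruitment pool. If the number does no work, two investigators can treat the same intermediate creatinine value differently, and a monitor has no usable limit against which to judge either decision.

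More than one laboratory may be involved. Section 6 (Visit 1) lets patients seen at the centre within the last 3 months complete screening and enrolment by virtual visit at the investigator's discretion. The caption to Fig. 7 in Section 3.1 has telemedicine patients give their safety bloods locally. The protocol names no reporting unit that would tie those results to the cut-off.

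**Working it through.** **Inputs**

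- Exclusion limit: creatinine above 2.0 mg/ml (Section 4.2).
- Conversion: 1 dL = 100 ml.
- Creatinine values in the population: none are given. I assume serum values of 1 to 50 mg/dL, a span meant to include advanced renal failure.

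The plan derives no figure from this limit, so there is no calculation of its own to reproduce. The check is a unit conversion and a comparison.

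**Step 1: the limit as written, on the mg/dL scale**

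2.0 mg/ml × 100 ml/dL = 200 mg/dL.

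In molar units, assuming a molar mass of 113.12 g/mol: 2.0 mg/ml = 2.0 g/L, and 2.0 / 113.12 = 0.01768 mol/L, or about 17,680 µmol/L.

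**Step 2: size of the unit effect**

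The same number read in mg/dL would be 2.0 / 100 = 0.02 mg/ml, about 177 µmol/L. The ratio is 2.0 / 0.02 = 100. This shows only how much hangs on the unit; it does not show which limit the sponsor meant.

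**Step 3: does the written limit trigger anywhere in the assumed range?**

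| Serum creatinine (mg/dL) | In mg/ml | Above 2.0 mg/ml? |
|---|---|---|
| 1 | 0.01 | No |
| 2 | 0.02 | No |
| 5 | 0.05 | No |
| 10 | 0.10 | No |
| 20 | 0.20 | No |
| 30 | 0.30 | No |
| 50 | 0.50 | No |

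The top of the range is 0.50 / 2.0 = 25% of the limit, so a value would have to be more than four times the highest one assumed before the number excluded anyone.

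**Step 4: what still excludes renal patients**

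Two routes remain in Section 4.2. One is the word *significant* applied to renal disease, which is not defined. The other is the investigator-judgement bullet, which is framed around findings on clinical examination and not around a laboratory value. Neither gives a limit that could be applied or audited uniformly.

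**The case against.** The strongest reply is that this is a suspected typing slip with little practical effect. The trial runs at a single centre that follows 340 living patients with this disease (Section 1.4), and a metabolic panel is taken before randomisation. Nobody there is likely to apply a limit of 200 mg/dL. That stands as a reason to rate the point low. It does not make the criterion correct, because the protocol is what a monitor checks against, and it allows virtual enrolment and local laboratories.

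A second reply is that the file may have been misread. The creatinine unit appears once, in an incomplete phrase, and in the machine-read text the blood pressure unit in neighbouring Section 4.1 comes out as mmHa. This also stands: it does not show that mg/ml is a reading error, but the source file has to be looked at first.

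Three stronger readings are tempting, and the documents support none of them.

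- *Renal patients are not excluded at all.* A reader might infer this from the conversion, but it is only the number that does no work. The wording and the judgement bullet can both exclude patients.
- *The 20% end-stage figure in Section 1.4 measures how many would be wrongly enrolled.* It describes patients surviving to age 25 who need dialysis or transplantation. They are the ones most likely to be called significant renal disease on the wording alone, and the trial enrols from age 10, which is a different denominator. The group that matters is patients above the intended limit whom an investigator would not already call significant, and the documents give no count of them.
- *The urinary norepinephrine result would be distorted.* This is a secondary endpoint (Section 3.3), and each patient is their own control (Section 8.6.1), so stable renal impairment would be present in all three periods and would not by itself favour one treatment. No section says that renal function affects this endpoint.

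**Conclusion.** Wrong as written, minor. The only numeric renal exclusion equals 200 mg/dL and never triggers for serum creatinine between 1 and 50 mg/dL. Renal exclusion therefore depends on an undefined adjective and on investigator judgement. End-stage disease would probably still be excluded that way; the exposed group is patients with intermediate impairment, who may be screened inconsistently. Its size cannot be estimated from the documents. Sample size, power and alpha do not change.

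The conclusion rests on two assumptions: that mg/ml is what the source file prints, and that the assumed creatinine range covers the population. The second is not delicate, given the fourfold margin. The first is decisive: if the source file shows a different unit, the point has to be looked at again. A reader might also infer that mg/dL was certainly intended. That is a reasonable guess, but the documents never use that unit for creatinine, so the intended unit and value remain for the sponsor to state.

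**What to change.** 1. Check the creatinine unit in Section 4.2 against the source file.
2. If it reads mg/ml there too, have the sponsor confirm the intended unit and value. No threshold is proposed here.
3. Correct Section 4.2 so that the limit is in the unit the laboratory reports, and complete the phrase so that it is clear what the limit defines.
4. Confirm that screening records apply that same unit, including values that come from local laboratories. For patients already enrolled, document which unit was applied.

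The cost is a correction of about one word in the protocol and a short check of screening records. No analysis, visit or sample-size figure changes.

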4.3 Subject Recruitment and Screening

Since most patient with FD take medications by opening capsules or crushing pills and flushing them through their gastrostomy, it is necessary to use carbidopa powder (rather then re-encapsulate the commercially available pills) to maintain treatment allocation concealment. Subjects randomized to receive placebo will receive an identical small capsule containing a matching powder, as we've previously done. Thirty subjects will be randomized. Randomization will be performed by the Investigational Pharmacy of NYU, and participants, caregivers and assessors will be blinded at all times from the randomization sequence. Randomization sequences will be generated using computer-based system using a permuted block design and the Investigational Pharmacy of NYU will dispense all medications and provide dosing instructions for titration down and washout between treatment arms (Appendix). Investigators will not be involved in specifying the actual doses patients take and will remain blind to treatment allocation throughout. The PI will have the capacity to break the blind and remove any patient from the study at anytime for safety concerns. To monitor compliance, patients will be instructed to return all unused study medications at study visits.

4.3.1 Assessment of mental capacity to consent.

There are few formal assessments of cognitive function in patients with FD. Published studies likely underestimate the frequency of cognitive impairment owing to the bias of only "higher functioning" patients being able to complete the cognitive assessment tests. We estimate that around 40% of patients have impaired cognitive function. Given this we anticipate difficultly completing recruitment goals without enrolling patients with diminished capacity, as this is a rare genetic disease. We have included the following measures to ensure adequate assessment of cognitive impairment and capacity are in place.

In order to provide a consistent method to assess subject capacity at screening, we will use a modified version of the Montreal Cognitive Assessment (MoCA), that has been specifically adapted for patients with FD. This a cognitive screening test is validated to assist health care professionals in evaluating cognitive impairment. It is a widely used and well accepted screening tool. It is a 30-point test which can be administered in less than 5 minutes. It evaluates short-term memory recall, visuospatial abilities, multiple aspects of executive functions, attention, concentration, working memory, language, and orientation to time and place. Because all patients with familial dysautonomia have some degree of impaired vision and proprioceptive dysfunction, the MoCA test has been adapted for this population to omit the items that depend on vision and coordination as not to underestimate their cognitive ability. Therefore, the Modified MoCA version that we will be using will rate cognitive deficits in a 25-point scale. Scores of 13 or less will be considered as moderate or severe cognitive impairment. Subjects with a score of 13 or less will be assumed not to have capacity and consent from a guardian will be required. If the patient has legal guardianship, a copy will be obtained and filed in the study chart. If legal guardianship has not been officially sought, a note to file will be made to document the consent process in the study chart to document a process of confirming of a Legally Authorized Representative.

Rational for inclusion of subject with diminished mental capacity to conent. This is the population that have a genetic lesion that impairs their blood pressure control and lead to early onset renal failure. Preliminary results show carbidopa has a beneficial effect on stabilizing the blood pressure and reducing this variability.

The MoCA will be administered by a licensed clinical investigator (MD or NP) and will be interpreted by a neurologist who is familiar with the specific needs of patients with FD ([name] or [name] [name]).

While it is not expected that subjects will lose the capacity to consent, should there be a change to the subject's mental status that the PI believes warrants reassessment of capacity, the modified MoCa test will be repeated.

4.3.2 Vulnerable Populations

Both children as well as adults without the capacity to consent for themselves will be enrolled in this study.

For Children:

- a. parental permission will be obtained from one parent
- b. Assent from the child will be sought, if possible

For cognitively impaired adults:

- a. Consent from the subject's legal authorized representative will be obtaind
- b. Assent from the subject will be sought, if possible

4.4 Early Withdrawal of Subjects

4.4.1 When and How to Withdraw Subjects

We have close connection to all FD families and do not anticipate that any patient will be lost to follow-up. To minimize the possibility of early withdrawals, we will make all patients fully aware of the study commitments prior to enrolling. We will make efforts to determine the reason for dropouts from the trial. In previous trials, patients with FD are occasionally unwilling to be randomized to placebo if they had experienced symptomatic improvement during an open label phase. In this trial, however, we do not anticipate dropouts due to unwillingness to be randomized to placebo, as the efficacy end-point is not primarily a symptom. Therefore, we do not anticipate problems retaining patients on the trial.

4.4.2 Data Collection and Follow-up for Withdrawn Subjects

Every attempt will be made to collect as much follow-up data as possible on subject which withdraw from the study.

5 Study Drug

5.1 Description

Carbidopa (DL- α -methyl- α -hydrazino-3, 4-dihydroxyphenyl-propionic acid, HMD, MK-486, Lodosyn ®) is a reversible competitive inhibitor of DOPA-decarboxylase that prevents dopamine formation outside the brain. ³³ It is structurally similar to DOPA except for one extra methyl (CH₃) and a hydrazine (N₂H₄) rather than an amino group. ³⁴ By forming a series of strong but ultimately reversible bonds with the enzyme's co-factor pyridoxine, carbidopa prevents the binding of DOPA and inhibits dopamine production. ³⁴ It has been used for many years to block the peripheral synthesis of dopamine in patients with Parkinson disease treated with L-DOPA. ³⁵

5.2 Treatment Regimen

Dose will be 100mg / 200 mg / placebo, oral administration, with a treatment duration of 1 month on each dose.

5.3 Method for Assigning Subjects to Treatment Groups

Double-blind, Randomized, cross-over design.

5.4 Preparation and Administration of Study Drug

The study drug will be stored and dispensed by the NYU investigational pharmacy. The NYU Investogational Pharmacy will maintain the subject randomization codes.

5.5 Subject Compliance Monitoring

At each study visit the study coordinator and reseach nurse will review compliance with each subject.

5.6 Prior and Concomitant Therapy

All concomitant medications will be collected

Concomitant medicines/therapies not permitted during the study are:

- MAO-inhibitors
- metoclopramide, domperidone, risperidone or other dopamine blockers
- tricyclic antidepressants
- neuroleptic drugs (haloperidol and chlorpromazine)

5.7 Packaging

Study drug will be packaged in 100 mg/ 200mg/ and matching placebo capsules and dispensed in a 30 day supply.

5.8 Blinding of Study Drug

Study is randomized Double-blind, the NYU Investigational Pharmacy will maintain the randomization codes for each subject.

5.9 Receiving, Storage, Dispensing and Return

5.9.1 Receipt of Drug Supplies

TownTotal Compounding Pharmacy will ship each subject's drug supply directly to the NYU Investogational pharmacy for storage and dispensing. Any unused medication will be returned to the Investigational pharmacy.

